#### 3.3.3 Criteria for Retreatment and Dose Delays

Treatment with alisertib will be repeated every 21 days. In order for a new cycle of therapy to begin, the patient must meet the following criteria:

- ANC must be  $\geq 1,500/\text{mm}^3$
- Platelet count must be  $\geq 75,000/\text{mm}^3$ .

If the patient fails to meet the above-cited criteria for retreatment, then initiation of the next cycle of therapy should be delayed for up to 1 week. At the end of that week, the patient should be re-evaluated to determine whether the criteria for retreatment have been met. Should treatment need to be delayed for more than 1 week (ie, a rest period of more than 21 days) because of incomplete recovery from treatment-related toxicity, the dose of alisertib will be reduced (Table 3-1Table 3-1) to 40 mg BID (Dose Level -1) when therapy resumes. A second dose reduction to 30 mg BID (Dose Level -2) may occur should treatment need to be delayed for more than 1 week because of incomplete recovery from treatment-related toxicity on the reduced dosage of 40 mg BID. Patients who require further dose reductions (Dose Level -3) will be taken off active treatment from the study and begin long-term follow-up. Should treatment need to be delayed for more than 2 weeks at any dose, therapy with alisertib will be discontinued.

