#### 1.5 Potential Risks and Benefits

Seven-hundred fourteen patients (excluding 13 patients from a company-sponsored, non-US IND study in Japan) have been treated with alisertib as of 29 March 2012. Clinical safety data includes experience from patients who received multiple cycles followed by treatment-free periods between each cycle, and from patients who reduced or discontinued treatment. Based on the available clinical data, drug abuse, dependency, and drug withdrawal effects were not observed.

To date, the observed risks associated with alisertib treatment, as detailed in the Safety Management Attachment of the IB, include: (1) reversible myelosuppression including leukopenia, neutropenia, febrile neutropenia, lymphopenia, thrombocytopenia, and anemia; (2) GI toxicity including stomatitis/mucositis/oral pain, nausea, vomiting, anorexia, abdominal pain, dyspepsia, diarrhea, and dehydration; (3) sedation, somnolence, confusional

state, disorientation (and associated memory loss), and gait disturbances; (4) alopecia; (5) asthenia/fatigue; (6) fever, (7) infection, (8) abnormal liver function tests (including aspartate transaminase [AST], alanine transaminase [ALT], bilirubin, alkaline phosphatase [ALP], and gamma glutamyl transferase [GGT]), and (9) rash, which may include bullous dermatitis, and palmar-plantar erythrodysaesthesia syndrome. While these toxicities are potentially associated with risk or discomfort to the patient, they are anticipated to be reversible.

To mitigate the inherent risks in clinical studies of alisertib, patients are evaluated frequently while they are receiving treatment.

Because alisertib inhibits Aurora A kinase, it is possible that alisertib may interfere with cancer growth and cause cancer cell death. Preclinical results indicate that alisertib is not a major substrate for efflux mechanisms that have been associated with cross-resistance between some types of anticancer agents. Thus, alisertib has potential through a potentially non-cross resistant pathway as compared to other agents the patients may have received. The clinical utility of these effects will be investigated in current and future studies.

This study will be conducted in compliance with the protocol, applicable regulatory requirements, and International Conference on Harmonisation (ICH) Good Clinical Practice (GCP), guidelines.

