#### 1.6 Study rationale and selection of drug doses

#### **Study Rationale**

There are 3 subtypes of aurora kinases (A, B, C), but only aurora kinase A and B are potential therapeutic targets. Aurora kinase A inhibition leads to mitotic delay, monopolar spindles, and chromosomal segregation errors whereas aurora kinase B inhibition causes dysfunctional cytokinesis, polyploidy, and apoptosis. Preclinical studies have strongly suggested aurora kinases to be a relevant therapeutic target in mesothelioma patients. Several independent groups have reported that aurora kinase gene expression is upregulated in mesothelioma tumor tissue and is a negative prognostic factor.[15, 16](also our group – publication pending). Crispi et al.[17] have also shown that inhibition of mesothelioma cell lines with an aurora kinase inhibitor ZM447439 led to cell growth arrest and was target specific. Kim et al. also reported on irradiated mesothelioma cells and how inhibition of surviving and aurora kinase B resulted in mitotic cell arrest.

There are several aurora kinase inhibitors under investigation. For aurora kinase A inhibitors, alisertib, (MLN8237, Millenium) are under investigation in phase I and II trials. Preliminary results suggest dose limiting toxicity to be myelosuppression and mucositis. Aurora kinase B inhibitors, GSK1070916A (GlaxoSmithKline) and AZD1152 (AstraZeneca) are also under investigation in phase I and II trials in solid tumors and AML.

Several additional phase I and II trials of pan-aurora kinase inhibitor trials are underway in solid tumors. Alisertib (International Proprietary Name, also known as MLN8237) is a selective small molecule inhibitor of Aurora A kinase that is being developed for the treatment of advanced malignancies.

To date, there are no aurora kinase inhibitor-specific mesothelioma trials and the proposed study would be the first to assess this class of drug in the disease. Based on the preclinical data reported in the literature and our own profiling studies, we believe that aurora kinase is a feasible and relevant target in mesothelioma therapeutics. Alisertib is a novel compound that has a reasonable safety profile and may show efficacy in this population of patients.

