#### 3.3.5 Dose Modifications for Non-Hematological Toxicities

If a patient experiences any of the following toxicities during the dosing period, dosing will be discontinued for the remainder of that cycle and the dose will be decreased 1 level for all subsequent cycles of treatment, and treatment may resume after drug-related toxicities have resolved to  $\leq$  Grade 1 or to baseline.

- Any Grade 3 nonhematological toxicity that is considered by the investigator to be related to study drug other than:
  - Grade 3 or greater nausea or emesis, or both, that occurs in the absence of optimal antiemetic therapy (5-hydroxytryptamine 3 [5-HT3] serotonin receptor antagonist);
  - Grade 3 or greater diarrhea that occurs in the absence of optimal supportive therapy with loperamide or a comparable anti-diarrheal;
  - o Grade 3 fatigue that lasts less than 1 week

• Grade 2 non-hematological toxicities that are considered by the investigator to be related to study drug and in the opinion of the investigator require dose reduction.

In general, study drug treatment should be discontinued if a patient experiences a Grade 4 toxicity. If, in the opinion of the investigator and Millennium it is in the patient's interest to continue therapy with alisertib, then after recovery from the toxicity or toxicities in question to  $\leq$  Grade 1 or to baseline values, the dose of alisertib should be reduced by at least 1 dose level with subsequent cycles of therapy.

When a dose reduction of alisertib is required, no re-escalation of dose will be permitted. If a patient requires more than 2 dose reductions, therapy with alisertib will be discontinued.

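### Section 3.3.3 conditions a new cycle on ANC and platelets only, and the Section 3.3.5 recovery threshold may not reach related Grade 3 non-hematologic toxicity, such as mucositis, that starts on Days 8-21

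*Combined protocol and SAP*

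**What the plan says.** Section 3.3.3 sets the conditions for redosing: "In order for a new cycle of therapy to begin, the patient must meet the following criteria". The list has two items, ANC of at least 1,500/mm³ and platelets of at least 75,000/mm³. The delay rules follow. A delay of more than 1 week for toxicity that has not fully resolved brings a reduction to 40 mg BID. The next step is permissive: "A second dose reduction to 30 mg BID (Dose Level -2) may occur". The outer limit is firm: "Should treatment need to be delayed for more than 2 weeks at any dose, therapy with alisertib will be discontinued".

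Section 3.3.5 holds the non-hematologic rule: "If a patient experiences any of the following toxicities during the dosing period, dosing will be discontinued for the remainder of that cycle". The dose then drops one level for later cycles, and "treatment may resume after drug-related toxicities have resolved to" Grade 1 or less, or baseline. The triggers are related Grade 3 toxicity, with exceptions for nausea/emesis, diarrhea and brief fatigue, and related Grade 2 toxicity that the investigator judges to need a reduction. Mucositis is not among the exceptions.

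On the drug's toxicity, the Study Rationale in Section 1.6 says: "Preliminary results suggest dose limiting toxicity to be myelosuppression and mucositis". Section 1.5 lists among observed risks "GI toxicity including stomatitis/mucositis/oral pain, nausea, vomiting, anorexia, abdominal pain, dyspepsia, diarrhea, and dehydration".

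**The concern.** Section 1.6 names two dose-limiting toxicities, and the Section 3.3.3 list has a criterion for only one of them. Recovery from the other depends on Section 3.3.5, and so on what the dosing period means.

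The stake is patient safety. If the term means Days 1-7, onset date alone decides which written rule applies. Related Grade 3 mucositis starting on Day 6 stops dosing, lowers the dose by one level and must recover to Grade 1 or baseline. The same event starting on Day 10 and unresolved on Day 22 triggers none of these. With adequate counts, another seven days at the same dose would break no written retreatment criterion.

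**Working it through.** No power or error-rate calculation applies. The check is day arithmetic and a comparison of the rules.

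**Inputs.** Cycle 21 days, dosing Days 1-7 (Section 3.3, Alisertib Administration). Treatment break Days 8-21 (Protocol Summary, Study Design and Methodology). Mean terminal half-life about 22 hours (Section 1.4).

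**The plan's own figure.** Section 3.3.3 says "Should treatment need to be delayed for more than 1 week (ie, a rest period of more than 21 days". Planned rest is 21 − 7 = 14 days; adding a 7-day delay gives 14 + 7 = 21 days. The figure is reproduced, and it works only if Days 8-21 count as rest.

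**Days outside the 3.3.5 trigger.**
- Dosing period = Days 1-7: 21 − 7 = 14 days, or 14/21 = 67% of the cycle.
- Dosing period = whole cycle: 0 days.

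**Drug still present after Day 7.** Five half-lives are 5 × 22 h = 110 h; 110/24 = 4.6 days after the last Day 7 dose, so about Day 12. On the narrow reading, roughly Days 8-12 fall outside the trigger while drug remains.

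**Wording that supports Days 1-7.**
- The Protocol Summary calls Days 8-21 a break, and the Section 3.3.3 rest-period arithmetic agrees.
- Section 3.4, on H2 antagonists, gives Day 7 as the example of when dosing ends.
- Stopping dosing for the rest of the cycle has an effect only while doses remain.

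**Wording that supports the whole cycle.**
- Section 3.3.4 uses the same phrase for Grade 4 cytopenias that persist beyond seven days in a row. That needs at least 8 days, and Days 1-7 provide 7.
- Section 3.3.5 excepts Grade 3 fatigue of under a week. Fatigue starting on Day 2 has lasted only 6 days by the end of Day 7, so applying the exception needs follow-up beyond it.
- The Section 3.3.3 delay rule refers to treatment-related toxicity generally, not only to counts.

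**Other rules that could cover a late related Grade 3 event.**

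| Rule | Does it require recovery before redosing? |
|---|---|
| 3.3.3 count criteria | No; cytopenias only |
| 3.3.3 delay rule | No; sets what follows a delay, not the non-hematologic grade that requires one |
| 3.3.2 | No; permits reduction or interruption for excessive toxicity |
| 3.3.5, Grade 4 sentence | No; does not reach Grade 3 |
| 3.7.3 | Interruption, for excessive sedation only |
| 3.8 and 3.9 | No; stopping or withdrawal, resting on judgment that toxicity is unacceptable or on a 2-week toxicity delay |

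**Persistence needed.** The next cycle is due on Day 22. An event starting on Day 10 must last 22 − 10 = 12 days to be unresolved then.

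**The case against.** The strongest reply is that the protocol's internal logic favors the whole cycle. On the narrow reading, the Section 3.3.4 item on prolonged Grade 4 cytopenia could never be met, and the fatigue exception would be hard to apply. Stopping the current cycle's doses is also only one limb of Section 3.3.5; the reduction for later cycles still works for a Day 10 event. Sections 3.3.2, 3.8 and 3.9 already give written authority to reduce, interrupt or stop, and a careful investigator would probably hold treatment.

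Much of this stands. It makes the gap conditional on one reading and shows that redosing is not compelled. It does not supply a definition, and those backstops leave the decision to judgment: no grade is written that obliges a hold for late onset.

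It is also fair that 14 of 21 days is a calendar count, not a risk, and that the statement about dose-limiting toxicity is described as preliminary. The documents give neither a rate nor an onset time for mucositis.

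A reader might infer a further defect in the Section 3.3.5 exceptions, because two of them say Grade 3 or greater while Grade 4 has its own sentence. The documents do not support that. The exceptions sit under the Grade 3 item and carve out of that item alone, so the extra words are surplus. Nor is there a case for relaxing the Section 3.3.3 reduction after a long delay for excepted events; that would remove an existing safeguard.

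**Conclusion.** The point holds as a gap in the written safety rules, conditional on reading the dosing period as Days 1-7. On that reading, related Grade 3 non-hematologic toxicity starting on Days 8-21 has no written hold, dose reduction or recovery grade before redosing. The same applies to Grade 2 toxicity that the investigator thinks needs a reduction. On the whole-cycle reading the window is zero days, and what remains is an undefined term and a retreatment list that does not point to Section 3.3.5.

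A reader might infer that patients will be redosed with unresolved mucositis, or that two thirds of such events escape the rules. Neither follows: investigators can hold or stop treatment, and no onset distribution is given. Nor does the protocol lack a non-hematologic recovery rule altogether; it has one, with an unclear trigger. Grade 4 toxicity, count recovery and excessive sedation are covered whatever the day of onset.

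The frequency is unknown, so no patient count is offered. The change is worth making because it is cheap and uses the protocol's own threshold. The two-stage design, sample size and error rates are unaffected.

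**What to change.** 1. In Section 3.3.5, and likewise in Section 3.3.4, replace *during the dosing period* with *at any time in the cycle, up to the start of the next cycle*, with dosing stopped if still ongoing.
2. Add to the Section 3.3.3 list: any non-hematologic toxicity that triggers Section 3.3.5 must have resolved to Grade 1 or less, or baseline, before the next cycle starts.

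Leave the Section 3.3.5 exceptions and the Section 3.3.3 delay and dose-reduction rules as they are.

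**Cost.** In the Schedule of Events as extracted, toxicity evaluation and blood counts share the same Day 1 marks, so the check needs no visit beyond those the count rule already needs. Some cycles will start later. Some patients with late-onset events will have a reduction that they would not have under the narrow reading, and Section 3.3.5 bars re-escalation. With the next cycle due on Day 22, a start after Day 29 (22 + 7) means reduction from 50 mg to 40 mg BID. At 40 mg, the Section 3.3.3 wording says only that a second reduction may follow. A delay beyond Day 36 (22 + 14) means discontinuation at any dose. The investigator and the drug supplier should confirm the clinical content.

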**Table 3-1 Table of Dose Adjustments** 

Dose Level	Dose	Schedule	Cycle Length
1	50 mg	PO BID day 1-7	21 days
-1	40 mg	PO BID day 1-7	21 days

#### Clinical Study Protocol # 2014-0497 10/28/2015

-2	30 mg	PO BID day 1-7	21 days
-3		Discontinue	

Level 1 is the starting dose.

#### 3.3.4 Dose Modifications for Hematological Toxicity

If a patient experiences any of the following hematological toxicities during the dosing period, dosing will be discontinued for the remainder of that cycle and the dose will be decreased 1 level for all subsequent cycles of treatment.

- Grade 4 neutropenia (ANC < 500 cells/mm³) lasting more than 7 consecutive days
- Grade 4 thrombocytopenia (platelet count < 25,000/ $\mu$ L) lasting more than 7 consecutive days
- Platelet count less than 10,000/μL at any time
- Grade 3 neutropenia with fever or infection, or both, where fever is defined as an oral temperature greater than 38.3°C
- Grade 3 thrombocytopenia with clinically significant bleeding

#### 3.3.5 Dose Modifications for Non-Hematological Toxicities

If a patient experiences any of the following toxicities during the dosing period, dosing will be discontinued for the remainder of that cycle and the dose will be decreased 1 level for all subsequent cycles of treatment, and treatment may resume after drug-related toxicities have resolved to  $\leq$  Grade 1 or to baseline.

- Any Grade 3 nonhematological toxicity that is considered by the investigator to be related to study drug other than:
  - Grade 3 or greater nausea or emesis, or both, that occurs in the absence of optimal antiemetic therapy (5-hydroxytryptamine 3 [5-HT3] serotonin receptor antagonist);
  - Grade 3 or greater diarrhea that occurs in the absence of optimal supportive therapy with loperamide or a comparable anti-diarrheal;
  - o Grade 3 fatigue that lasts less than 1 week

• Grade 2 non-hematological toxicities that are considered by the investigator to be related to study drug and in the opinion of the investigator require dose reduction.

In general, study drug treatment should be discontinued if a patient experiences a Grade 4 toxicity. If, in the opinion of the investigator and Millennium it is in the patient's interest to continue therapy with alisertib, then after recovery from the toxicity or toxicities in question to  $\leq$  Grade 1 or to baseline values, the dose of alisertib should be reduced by at least 1 dose level with subsequent cycles of therapy.

When a dose reduction of alisertib is required, no re-escalation of dose will be permitted. If a patient requires more than 2 dose reductions, therapy with alisertib will be discontinued.

#### 3.3.6 Packaging and Labeling

The study drug, provided by Millennium, will be labeled and handled at the investigative site as open-label material; packaging labels will fulfill all requirements specified by governing regulations. Alisertib will be supplied as ECT in 10 mg strength. The 60-cc HDPE bottles will have a child-resistant cap and be labeled for take-home use. Patients will receive instructions for home use of alisertib, including the requirement that Alisertib be administered as intact tablets.

#### 3.4 Excluded Concomitant Medications and Procedures

The following medications and procedures are prohibited during the study:

- Any antineoplastic therapy other than alisertib
- Alternative therapy, including palliative radiotherapy, for definitive treatment of the patient's malignancy
- Any investigational anti-cancer therapy other than alisertib.
- Requirement for administration of any proton pump inhibitor. Use of any PPI in
  either continued or intermittent use will be prohibited during the conduct of the
  study and patients must discontinue any use of PPI within five days prior to the first
  dose of alisertib. Patients may be administered alternative agents to manage gastric
  acidity or reflux (eg, H2 receptor antagonists, antacids) with exceptions described
  below.

- Histamine-2 (H2) receptor antagonists are not permitted from the day prior (Day 1) through to the end of alisertib dosing (e.g., Day 7), except as required for premedication for a protocol-specific agent (eg, taxane).
- Enzyme inducers, such as the enzyme-inducing antiepileptic drugs phenytoin, carbamazepine or phenobarbital, or rifampin, rifabutin, rifapentine or St. John's wort within 14 days prior to the first dose of alisertib.

#### 3.5 Permitted Concomitant Medications and Procedures

Myeloid growth factors to treat patients with neutropenia according to the American Society of Clinical Oncology (ASCO) Guidelines. When applicable (eg, Phase 1 studies) use of myeloid growth factors should be avoided (if medically appropriate) in Cycle 1 until patients have developed a DLT or dose-limiting Grade 4 neutropenia. Antiemetic agents may be administered at the discretion of the investigator but are not commonly required as a prophylactic agent. All other manifestations of the patient's malignancy should be treated at the discretion of the investigator.

Antacids are permitted; however, they should be administered more than 2 hours before or 2 hours after administration of alisertib.

Medications with potential CNS effects are not prohibited in this study, but it is recommended that their use be minimized to avoid confusion in the interpretation of CNS effects should they occur during the course of treatment with alisertib. Because of alisertib's structural and pharmacological similarity to the benzodiazepines, concomitant therapy with benzodiazepines is discouraged but not prohibited.

In appropriate settings, such as combinations with agents known to produce frequent thrombocytopenia, restricted uses of anticoagulants should be considered.

All other medical conditions should be treated at the discretion of the investigator in accordance with local community standards of medical care.

#### 3.6 Precautions and Restrictions

Patients are to be instructed to limit the use of alcohol while enrolled in this study. Patients should consume no more than 1 standard unit of alcohol per day during the study and for 30 days from the last dose of alisertib. A standard unit of alcohol is defined as a 12 oz beer (350 mL), 1.5 oz (45 mL) of 80-proof alcohol, or one 6-oz (175 mL) glass of wine.

It is not known what effects alisertib has on human pregnancy or development of the embryo or fetus. Therefore, male patients should avoid impregnating a female partner.

Male patients, even if surgically sterilized (ie, status post-vasectomy) must agree to one of the following:

Practice effective barrier contraception during the entire study treatment period and through four months after the last dose of study drug, or completely abstain from heterosexual intercourse.

#### 3.7 Management of Clinical Events

#### 3.7.1 Nausea and Vomiting

Prophylactic antiemetic therapy will not be used in this study unless it becomes clear that alisertib causes acute nausea and vomiting. If prophylactic antiemetic therapy is needed, 5-HT3 receptor antagonists (without corticosteroids) should be tried first. Because of the potential of benzodiazepines to cause sedation, the use of benzodiazepines for antiemetic prophylaxis should be reserved for patients who cannot be satisfactorily managed otherwise.

Although this study will not initially employ prophylactic antiemetics, there is no prohibition against antiemetic use in the management of a patient who develops nausea or vomiting, or both.

